6.4 Accountability Procedures for the Study Product

The research pharmacy will be responsible for maintaining logs (paper or electronic) to document the acquisition and dispensing of Erenumab and placebo. The pharmacy will also be responsible for maintaining and monitoring storage conditions. The logs and records of storage conditions will be reviewed by the study clinical monitor during periodic monitoring visits.

6.5 Assessment of Subject Compliance with Study Product Administration

Participants will receive the medication or placebo injection by a trained study staff member once a month on Visits 1, 2 and 3.

Between visits, study personnel will contact participants by telephone to assess study drug tolerance (AEs), and to remind them when they are scheduled for another dosage.

6.6 Concomitant Medications/Treatments

At the Screening and Baseline Visit (Visit 0), information concerning prior and concomitant medications for the previous 30 days will be collected, including name(s) of medication(s), total daily dose, start date, stop date (if applicable), and primary reason for use. Similarly, information about prior and concomitant therapies, including injection therapy, acupuncture, physical therapy, and intraoral appliance therapy, will also be collected for all participants for the 30 days prior to the Screening and Baseline Visit. The

concomitant medication/therapy information will also be updated at subsequent study visits (Visits 1-5).

6.6.1 *Allowable Pain Medication*

6.6.2 *Prescription medications*

Participants who enter the study already on a daily regimen of a prescription medication for pain management will be encouraged to continue that regimen throughout the study and should not be modified. The usage of all prescription medications for pain during the study will be recorded and quantified at each visit.

Rescue medications will be defined as allowed over-the-counter analgesics used for treatment of TMD pain. In case a patient presents pain, the medications described below may be used:

6.6.3 *Over-the-counter medications*

NSAIDs are very often used to manage pain in TMD patients and for other pain conditions. Participants use of short-acting non-prescription analgesics such as NSAIDs, acetaminophen or aspirin during the study, will be recorded and quantified at each visit, and the usage will be classified as either episodic or daily.

Episodic use of non-prescription analgesics will be defined as use for no more than 2 consecutive days and for no more than 18 days from baseline to visit 4. This type of analgesics should not be used for more than 2 days a week prior to Baseline and a week prior to V4, when the exploratory outcome is assessed.

If a participant is taking an over-the-counter medication daily for management of any type of pain or for prophylaxis of myocardial infarction or stroke, the participant will be encouraged to continue the same usage of that medication throughout the study.

6.6.4 *Nonpharmacologic Therapy*

During the course of the study, participants will not be restricted in the use of non-pharmacological therapies, with the exception of acupuncture, physical therapy and splint therapy. If a participant starts these therapies for the management of pain during the study, the use of these therapies will be recorded in the eCRF and the patient will need to be withdrawn of the study. The use of intraoral appliances at night only is allowed if was started at least 30 days prior to Screening and Baseline V0.

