5.1 Subject Inclusion Criteria

In order to be eligible to participate in this study, an individual must meet all of the following criteria:

1. Provide signed and dated informed consent form
2. Is between 18 and 65 years of age (inclusive; male or female and any race or ethnicity)
3. Meets diagnostic criteria for TMD: Myalgia with or without arthralgia
 - The participant must meet 2 criteria relating: 1) reported pain, ache or tenderness in the face, jaw/mandible, pre-auricular area, inside the ear or temple that it is modified by TMJ biomechanics. 2) finding(s) of TMD myalgia according to the classification DC/TMD criteria.
4. Has experienced facial pain and/or pain with TMJ biomechanics for the last 3 months episodically or unremitting
5. Has experienced facial pain for at least 10 days of the last 30 days prior to Baseline Visit (Visit 0)
6. Prior to randomization, has been compliant 80% with the entries in the Daily Symptom Diary within the baseline period and reported an average pain level ≥ 30 on a numerical rating scale (0-100) in the DSD, or has experienced a pain level ≥ 30 on the same scale for at least 3 days in the week prior to Visit 1.
7. If taking a prescription medication daily for the management of pain (taken for at least 30 days before baseline), agrees to continue the daily use of the medication throughout the study at the same dosage.

8. If taking prescription medication, opioid medication or OTC medications as needed or episodically for the management of TMD pain agrees to discontinue its use prior to the Screening and Baseline Visit.
 - Rescue medications will be defined as allowable over-the-counter analgesics used for treatment of TMD pain. In case a patient presents pain during the study, only it is allowed the use of OTC medications as a “rescue” and as described on section 6.6.3: Participants use of short-acting non-prescription analgesics such as NSAIDs, acetaminophen or aspirin during the study, will be recorded and quantified at each visit, and the usage will be classified as either episodic or daily. Episodic use of non-prescription analgesics will be defined as use for no more than 2 consecutive days and for no more than 18 days from baseline to visit 4.
 - This type of analgesics should not be used for more than 2 days a week prior to Baseline and a week prior to visit 4, when the exploratory outcome is assessed (cytokine release assay).

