5.4 Treatment Assignment Procedures

This will be a conventional factorial design, randomized, double-blinded clinical trial with two parallel arms to evaluate efficacy of Erenumab:

- Erenumab, a monoclonal antibody medication that inhibits the CGRP pathway, which is FDA-approved for the prevention of migraine in adults. The comparison will be to placebo.

5.4.1 *Randomization Procedures (if applicable)*

Extensive screening procedures of potential participants to determine their eligibility based on the inclusion and exclusion criteria will be carried out prior randomization. Participants who do not meet these criteria will not be enrolled in the study.

Randomization visit will be within 7 days after Visit 0, eligibility will be further confirmed based on completion of Daily Symptom Diaries and pain intensity score. Qualified participants will be randomly assigned to one of the two arms of the study in a 1:1 ratio:

- 1) Investigational arm: Erenumab: N= 30 participants
- 2) Placebo: N=30 participants

Randomization

Subjects will be randomized to the investigational treatment group (Erenumab) or the placebo group using a blocked randomization scheme. The examiners and patients will be blind to the group assignment. Randomization will be done by Investigational Drug Services (IDS/Research pharmacy). There will be a 1:1 ratio of treatment to placebo participants.

Blinding

Blinding will be done by Investigational Drug Services (IDS). The PI and study staff will be blind to what the participant is receiving.

Treatment/randomization codes

IDS will be responsible for randomization of participant assignment to either the study medication or placebo groups. IDS will use a random number generation program to determine assignment.

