7.2 Screening and Baseline Visit (Visit 0, 4 weeks baseline period)

- Obtain and document consent from subject participation in the study.
- Obtain signed Health Insurance Portability and Accountability Act (HIPAA)

Authorization

- Review medical/dental history to determine eligibility based on inclusion/exclusion criteria.
- Take blood pressure and collect weight and height.
- Review medications history to determine eligibility based on inclusion/exclusion criteria.
 - Record concomitant medications and therapies
- Administer Symptom Inventory
- Perform TMD examination (Including Panoramic X-Ray).
- Perform Pressure Pain examination

- Collect blood for Cytokine release assay
- Perform urine pregnancy test (in women with childbearing potential)
- Provide instruction to complete 6 outcome measure questionnaires in paper or electronically for review next visit
- Provide instruction to complete Daily Symptom Diaries electronically or in paper dispense forms.

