15.3 Informed Consent Process

Potential participants may be contacted by telephone or in person for pre-screening; in some instances, it may also be conducted simultaneous with the Screening and Baseline Visit (Visit 0) or during a scheduled visit to the Brotman Facial Pain Clinic or Oral Surgery Clinic. Written informed consent will be obtained at Visit 0 in where will be evaluated eligibility, obtain demographics, medical history, medication information, and perform evaluations and provide the daily symptoms diaries and then schedule visit 1.

Informed consent is a process that is initiated prior to the individual agreeing to participate in the study and continues throughout study participation. Extensive discussion of risks and possible benefits of study participation will be provided to subjects and their families, if applicable. A consent form describing in detail the study procedures and risks will be given to the subject. Consent forms will be approved by the sponsor (UMB) IRB, and the subject is required to read and review the document or have the document read to him or her.

The investigator or designee will explain the research study to the subject and answer any questions that may arise. The subject will sign the informed consent document prior to any study-related assessments or procedures. Participants will be given the opportunity to discuss the study with their surrogates or think about it prior to agreeing to participate. They may withdraw consent at any time throughout the course of the study. A copy of the signed informed consent document will be given to subjects for their records. The rights and welfare of the subjects will be protected by emphasizing to them that the quality of their clinical care will not be adversely affected if they decline to participate in this study.

The consent process will be documented in the clinical or research record.

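### Section 8.2.2 names two different baseline cytokine draws (Visit 0 and Visit 1); at Visit 0 the 2-day analgesic limit before the sample is checked by recall, before Visit 4 by diary (minor, exploratory endpoint only)

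*Combined protocol and SAP*

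**What the plan says.** **The limit and its purpose.** Section 6.6.3 says of episodic over-the-counter analgesics: "This type of analgesics should not be used for more than 2 days a week prior to Baseline and a week prior to V4". The matching bullet under criterion 8 in 5.1 ties the limit to the time "when the exploratory outcome is assessed (cytokine release assay". I read it as no more than 2 days of use in the 7 days before each sample. Criterion 5 equates the Baseline Visit with Visit 0.

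**How it is checked at baseline.** The limit sits under an inclusion criterion, and 5.4.1 says "Participants who do not meet these criteria will not be enrolled in the study". The Visit 0 list in 7.2 includes "Review medications history to determine eligibility based on inclusion/exclusion criteria". Section 6.6 describes a 30-day medication history taken at that visit, "including name(s) of medication(s), total daily dose, start date, stop date (if applicable), and primary reason for use".

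**When the sample is drawn.** The Visit 0 list also contains "Collect blood for Cytokine release assay". Section 8.1, Appendix A and the first bullet of 8.2.2 agree on Visits 0 and 4. A later bullet of 8.2.2, on amount and frequency, says visits 1 and 4. The Visit 1 list in 7.3.1 has no blood draw.

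**Consent and diary.** Section 15.3 places written consent at Visit 0: "The subject will sign the informed consent document prior to any study-related assessments or procedures". The diary, which records pain medication each day (8.1), is explained at Visit 0, and its baseline period follows that visit (4, 7.2.1).

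**The concern.** There are two linked problems. Staff who follow the visit lists and staff who follow the later 8.2.2 bullet would take the baseline sample at different visits. The Visit 1 instruction also does not say that the sample must come before the injection.

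The protocol has also decided that recent analgesic use matters for this assay, yet it controls the two samples differently. The week before Visit 4 is recorded day by day. The week before Visit 0 is over before the participant has consented or has a diary. Pre-screening may take place on the same day as Visit 0, and 7.1 does not say that the limit is explained then.

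At stake is the exploratory objective, change in cytokines. Unequal control of the two samples, and baselines taken at different times, add variability to the arm comparison. They can also shift an apparent change within an arm for reasons unrelated to treatment.

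**Working it through.** The plan gives no figure to reproduce. The check is a timeline comparison.

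**1. Baseline draw visit, by place in the protocol.**
- Visit 0: 7.2, 8.1, first bullet of 8.2.2, Appendix A.
- Visit 1: later bullet of 8.2.2.
- No draw at Visit 1: 7.3.1.

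Visit 0 is the likely intent, four places to one, but the specimen section itself is contradictory.

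**2. Diary coverage of the 7 days before each possible sample.**
- Visit 0: the diary has not started, so 0 of 7.
- Visit 4 (Day 84): Days 77 to 83 lie inside the treatment-phase diary, so 7 of 7.
- Visit 1: Section 4 sets a 28-day baseline period after Visit 0, with Visit 1 up to a week after randomisation. If the diary stopped at the end of the baseline period and Visit 1 came g days later (g from 0 to 7), coverage would be 7 − g, that is 7 down to 0. If the diary continues to Visit 1, it is 7 of 7. Criterion 6 uses pain levels "for at least 3 days in the week prior to Visit 1", which suggests that it continues, but 7.2.1 refers to the week before randomisation. The supported statement is therefore up to 7 of 7, conditional on the diary running through the gap.

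**3. Completeness of the diary.** Eligibility needs 80% compliance: 0.80 × 28 = 22.4, so 23 days (23/28 = 82.1%; 22/28 = 78.6% fails). Up to 28 − 23 = 5 days may be missing. If all fell in the sample week, only 7 − 5 = 2 of its days would be recorded. Missing days must therefore be asked about even when the diary covers the week.

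**4. Is the sample-week limit redundant?** Episodic use is otherwise capped at 2 consecutive days and 18 days from baseline to Visit 4. The most days in 7 with no run longer than 2 is 5 (use, use, off, use, use, off, use). The 2-day limit therefore does real work.

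**5. Time from baseline sample to first dose (Visit 4 is 84 days after Visit 1).**
- 28-day baseline period plus up to 7 days to Visit 1: 28/(28+84) = 25.0% to 35/(35+84) = 29.4% of the interval to Visit 4.
- Appendix A, Visit 0 placed 1 to 3 weeks before Visit 1: 7/(7+84) = 7.7% to 21/(21+84) = 20.0%.
- Visit 1 before the injection: 0.

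The two instructions in 8.2.2 thus give baselines 7 to 35 days apart, depending on which schedule text applies.

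**The case against.** The strongest reply is that the baseline week is controlled. Criterion 8 also asks as-needed users to agree to stop before Visit 0. Pre-screening uses a script aimed at the inclusion criteria and can take place up to two weeks earlier. Checking a one-week limit by history is ordinary screening practice. The list of history fields in 6.6 opens with a word showing that it need not be exhaustive, and the case report forms and Manual of Procedures, which are not in the documents, may count days of use. Visit 0 is the draw visit in four places, so the smallest repair is to one bullet. Moving the draw would touch more sections and, once enrolment has begun, would itself create mixed baseline time points.

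Most of this stands, and it sets the weight of the point. Left over are the contradiction in 8.2.2 and the difference in method between the two sample weeks. Agreeing to stop is not a record of stopping, and a separate 2-day limit implies that some use was expected.

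Three stronger readings are tempting and not supported:
- *The limit cannot be checked at baseline, or days of use cannot be counted.* It is an eligibility condition reviewed at Visit 0. The text shows only that the check looks back and that no day count is listed.
- *The cytokine comparison is biased.* Recall error before Visit 0 arises before randomisation and blinding is maintained, so it should be unrelated to arm.
- *A Visit 1 draw guarantees full diary coverage.* That depends on the diary continuing after randomisation, which the text does not clearly say.

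Nor would a minimum detectable difference for the cytokine endpoint help: it would describe the sample size, not this defect.

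**Conclusion.** The point holds and is minor. Section 8.2.2 needs correcting in any case. With a Visit 0 draw, the protocol's own analgesic limit is checked by recall (0 of 7 days in the diary), while the week before Visit 4 lies inside the diary (7 of 7).

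The consequence is confined to the exploratory cytokine endpoint: added noise in the arm comparison, and possible distortion of any within-arm change. The documents give no basis for sizing that noise, and none is claimed. The randomised comparison stays unbiased, provided the baseline sample is taken before the first injection, and the primary comparison is unaffected.

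This rests on the protocol text alone and on reading the limit as 2 days in the week before each sample. A day count in the case report forms would remove most of the recall concern but not the contradiction.

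**What to change.** State one baseline draw time in 7.2, 7.3.1, 8.1, 8.2.2 and Appendix A.

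**Preferred: Visit 1, before the first injection.**
- State that the diary continues up to Visit 1.
- Reword 6.6.3 and the criterion 8 bullet so that episodic or rescue over-the-counter analgesics are used on no more than 2 of the 7 days before Visit 1 and 2 of the 7 days before Visit 4. Daily users continue unchanged.
- Record the number of analgesic days in both weeks, asking about missing diary days at the medication update already done at those visits. If the limit is exceeded, take the sample and record the count.
- Leave the criterion 8 agreement to stop before Visit 0, and criterion 9, as they are.
- Keep any samples already drawn at Visit 0 and flag them as a different time point.

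**Minimum: keep Visit 0.** Correct the 8.2.2 bullet, and record analgesic days in the previous 7 days at Visits 0 and 4.

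**In either case,** compare arms on the Visit 4 value adjusted for the baseline value, and do not treat within-arm tests as evidence of effect.

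**Cost.** The preferred option needs wording changes and no extra visit, and spares people who fail diary eligibility a 10–15 ml draw. The sample-week limit would become a recorded sampling condition instead of an eligibility test. It would also restrict rescue use in or just after the last baseline diary week, before treatment and equally in both arms. On average this is a small tightening, since the 18-day cap already works out at 18/(119/7) = 1.06 to 18/(91/7) = 1.38 days per week, although a single week may otherwise reach 5 days. The minimum option costs one corrected bullet and one question at each of two visits.

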7 STUDY SCHEDULE

7.1 Pre-Screening

Pre-screening (0-2 weeks, Day -15 to -1)

Potential participants may be contacted by telephone or in person for pre-screening; in some instances, it may also be conducted simultaneous with the Screening and Baseline Visit (Visit 0) or during a scheduled visit to the Brotman Facial Pain Clinic or Oral Surgery Clinic.

After contacting potentially eligible participants and after obtaining their verbal consent we will proceed to conduct a pre-screening interview with questions designed to identify participants with a high probability of meeting inclusion criteria. This interview will be conducted by trained study staff using a standard script. For the potential participants who express interest in the study, documentation of verbal consent, the pre-screening date, and screening ID will be recorded. In addition, an in-clinic Screening and Baseline Visit (Visit 0), will be scheduled after 0-2 weeks from the date of the pre-screening interview.

7.2 Screening and Baseline Visit (Visit 0, 4 weeks baseline period)

- Obtain and document consent from subject participation in the study.
- Obtain signed Health Insurance Portability and Accountability Act (HIPAA)

Authorization

- Review medical/dental history to determine eligibility based on inclusion/exclusion criteria.
- Take blood pressure and collect weight and height.
- Review medications history to determine eligibility based on inclusion/exclusion criteria.
 - Record concomitant medications and therapies
- Administer Symptom Inventory
- Perform TMD examination (Including Panoramic X-Ray).
- Perform Pressure Pain examination

- Collect blood for Cytokine release assay
- Perform urine pregnancy test (in women with childbearing potential)
- Provide instruction to complete 6 outcome measure questionnaires in paper or electronically for review next visit
- Provide instruction to complete Daily Symptom Diaries electronically or in paper dispense forms.

7.2.1 Randomization

Prior randomization, the participant to be eligible is required to have 80% compliance with the Daily Symptom Diary for the baseline period after visit 0 and reported an average pain level ≥ 30 on a numerical rating scale (0-100) or had experienced a pain level ≥ 30 on the same scale for at least 3 days the week before randomization. Participants then will be randomly assigned to one of two groups (Erenumab or placebo) and will be scheduled for Visit 1. Visit 1 should be scheduled within a week after randomization

7.3 Treatment Visits

Visits 1-4

Participants will be receiving 3 cycles of either erenumab or placebo in visits 1-3. On visit 4, treatment will not be delivered but assessments will be performed.

7.3.1 First treatment cycle (Visit 1, Day 0)

- Review Daily Symptom Diaries in eCRF or collect and review it in paper forms
- Review medical history
- Record concomitant medications and therapies
- Take blood pressure and collect weight
- Administer the Symptom Inventory
- Assess and record adverse events (AEs)
- Perform TMD examination
- Perform Pressure Pain examination

- Perform urine pregnancy test (in women of childbearing potential)
- Review 5 questionnaires from Visit 0 in eCRF or collect and review the paper forms
- Provide instruction to complete 6 new outcome measure questionnaires in paper or electronically for review at Visit 2.
- Provide instruction to complete Daily Symptom Diaries electronically or provide them in paper forms
- Deliver the injection of the study drug or placebo
- Schedule next visit

7.3.2 Visit 2, 2nd treatment/cycle (Day 28/ 4 weeks after Visit 1)

- Review Daily Symptom Diaries in eCRF or collect and review it in paper forms
- Assess compliance with Daily Symptom Diaries
- Review medical history
- Record concomitant medications and therapies
- Take blood pressure and collect weight
- Administer the Symptom Inventory
- Assess and record adverse events (AEs)
- Perform TMD examination
- Perform Pressure Pain examination
- Perform urine pregnancy test (in women of childbearing potential)
- Review 6 questionnaires from Visit 1 in eCRF or collect and review the paper forms
- Provide instruction to complete 6 new outcome measure questionnaires in paper or electronically for review at Visit 3.

- Provide instruction to complete Daily Symptom Diaries electronically or provide them in paper forms
- Deliver the injection of the study drug or placebo
- Schedule next visit

7.3.3 Visit 3, 3rd and final treatment cycle (Day 56/ after 4 weeks from Visit 2)

- Review Daily Symptom Diaries in eCRF or collect and review it in paper forms
- Assess compliance with Daily Symptom Diaries
- Review medical history
- Record concomitant medications and therapies
- Take blood pressure and collect weight
- Administer the Symptom Inventory
- Assess and record adverse events (AEs)
- Perform TMD examination
- Perform Pressure Pain examination
- Perform urine pregnancy test (in women of childbearing potential)
- Review 5 questionnaires from Visit 2 in eCRF or collect and review the paper forms
- Provide instruction to complete 6 new outcome measure questionnaires in paper or electronically for review at Visit 4.
- Provide instruction to complete Daily Symptom Diaries electronically or provide them in paper forms
- Deliver the injection of the study drug or placebo
- Schedule next visit

7.3.4 Visit 4, assessment of last treatment cycle (Day 84/4 weeks after Visit 3)

- Review Daily Symptom Diaries in eCRF or collect and review it in paper forms
- Assess compliance with Daily Symptom Diaries
- Review medical history
- Record concomitant medications and therapies
- Take blood pressure and collect weight
- Administer the Symptom Inventory
- Assess and record adverse events (AEs)
- Perform TMD examination
- Perform Pressure Pain examination
- Collect blood for Cytokine release assay
- Perform urine pregnancy test (in women of childbearing potential)
- Review 5 questionnaires from Visit 3 in eCRF or collect and review the paper forms
- Schedule next visit
- Administer the <intervention>.
- Record subject's compliance with <intervention>.
- Following administration of <intervention>
 - Assess vital signs
 - Administer Symptoms Questionnaire

7.4 Follow up and final Study Visit, Visit 5 (Day 112/ 4 weeks after Visit 4)

- Review Daily Symptom Diaries in eCRF or collect and review it in paper forms
- Assess compliance with Daily Symptom Diaries
- Review medical history
- Record concomitant medications and therapies

- Take blood pressure and collect weight
- Administer the Symptom Inventory
- Assess and record adverse events (AEs)
- Perform TMD examination
- Perform Pressure Pain examination
- Perform urine pregnancy test (in women of childbearing potential)
- Review 5 questionnaires from Visit 4 in eCRF or collect and review the paper forms
- Provide final instructions to subject (in case of AE showing later)
- Complete a disposition form

